7.2 HCQ Pharmacokinetics

7.2.1 Clinical Pharmacology of HCQ and rationale for population PK Studies

Preclinical studies have demonstrated that high nanomolar to low micromolar concentrations of CQ or HCQ are needed to effectively inhibit autophagy resulting in the accumulation of AV in cancer cells. In order to characterize autophagy inhibition in patients receiving HCQ in combination B, PK measurements will be correlated with PD measurements to determine the exposure of HCQ that is clinically achievable in this population and the effect on autophagy at these concentrations. Comparison of PK measurements of HCQ when given in this combination regimen to previously reported PK measurements of HCQ alone, will also identify potential drug-drug interactions that require further study. All PK analyses will be done by [name] at the University of Arizona through a subcontract and MTA.

The PK properties of HCQ as a single agent have been extensively described in patients with rheumatoid arthritis. In one study patients received HCQ at doses of 400 mg, 800 mg or 1200

mg po daily (Carmichael et al., 2003). HCQ is metabolized by the p450 enzyme system into a number of active metabolites. The investigators measured the blood levels of HCQ, and its active metabolites desethylhydroxychloroquine (DHCQ), desethylchloroquine (DCQ) and bisdesethylchloroquine (BDCQ). Despite differences in interindividual PK measurements, HCQ concentration increased linearly in the blood of patients with dose. In this study peak concentrations of HCQ approach 2-3 μ M in higher dose cohorts supporting the need for dose escalation of HCQ beyond the 400 mg po daily dose that is commonly prescribed for rheumatoid arthritis patients. A clear dose-response relationship was observed between peak HCQ, DHCQ, and BCQ concentrations and improvement in arthritis. In addition a clear association between peak HCQ concentrations and GI toxicity, mainly nausea and vomiting, was observed. The mean elimination half-life of each of these metabolites is between 30-50 days. Due to budgetary constraints binimetinib PK studies are not planned. If there is a significant difference between HCQ exposure in this study compared to previous studies and there is sufficient activity to warrant a larger phase II study a more complete drug-drug interaction study can be conducted as part of that study.

A population PK approach has been used in the past for HCQ, and has several advantages compared to a more traditional intensive sampling PK study design. First, it allows the analysis of relatively sparse data which can be more easily obtained over time in an outpatient setting. Furthermore, a population PK analysis provides estimates of population central PK parameter values, as well as estimates of inter- and intra-patient variability in HCQ blood concentrations. To obtain these estimates, samples must be obtained from each patient on more than one occasion. In patients that remain on study for this time, blood concentration determinations during the late phases of the study will be important to derive PK parameter estimates that are most representative of those at steady-state conditions. Samples obtained during initial and late phases of the study will be used to build the population PK model.

7.2.2 Pharmacokinetic Sample Collections

A sparse sampling approach will be applied to all patients that consists of blood collection pretreatment, and monthly after start of B+HCQ. A 5 mL venous blood sample for determination of HCQ in anticoagulated whole blood will be collected in a heparinized green-top tube and placed on ice until it can be aliquotted into three polypropylene tube and stored at -80°C. Centrifugation is not required. All specimens will be labeled with the patient's assigned study number, day on study, date and time. A separate log of patient samples will also record this information, and in addition, the time of last HCQ and last binimetinib dose, and time of last meal, and a description of concomitant medications at the time of collection. The PK blood draw should be scheduled for the convenience of the subject. For these sparse sampling collections, patients will be asked to continue their drug dosing as scheduled and not hold any doses even on days of blood draws. For HCQ, one sample will be collected during each visit for the first year that will also ensure random collections at times both pre- and post-HCQ dose. The time of last administration of HCQ and the time of the blood draw should be recorded.

7.2.3 Bioanalytic Methods and PK analysis.

The bioanalytic method and pharmacokinetic analysis will be performed at the University of Arizona under the aegis of [name].

Hydroxychloroquine. Whole blood concentrations of HCQ and its metabolites (DHCQ, DCQ, BDCQ) will be measured using a modification of published high-performance liquid chromatography methods using fluorescence and tandem mass spectrometry detection (HPLC-MS/MS). CQ will be used as the internal standard. Briefly, the blood will be alkalinized and then subjected to ether extraction to extract HCQ and its metabolites. The ether extracts will be

evaporated to dryness and reconstituted in mobile phase. A methanol-based mobile phase will be used to separate the analytes. Elution of the analytes will be analyzed simultaneously using fluorescence and mass detection with a Varian LC 1200 triple quadrupole mass spectrometer. Whole blood concentrations of HCQ will be calculated for each sample based on a standard curve of peak area ratios of the drug and internal standard (CQ).

A population PK model will be developed to define the full HCQ PK profile over the entire patient population, which includes patients receiving HCQ in conjunction with other agents under investigation. In the population approach, data from individual patients are treated as random samples from a larger population. Estimates of the population central values for HCQ, as well as inter- and intra-patient variability are determined using nonlinear mixed-effects modeling software (NONMEM). The population PK parameters that will be estimated using this approach are apparent clearance (CI/F) and volume of distribution of the central compartment (Vd/F). Since the absolute bioavailability of HCQ (F) cannot be calculated for oral dosing alone, bioavailability will be represented by a fixed constant for each of the parameter estimates. Comparison of these PK parameters of HCQ when given in combination with D+T to previously reported PK parameters of HCQ alone may identify a potential drug interaction that requires further study.

The results from the population analysis will be used as prior information to obtain Bayesian estimates of each individual patient's PK parameters (CI and Vd) from his/her blood HCQ concentrations. The Bayesian approach incorporates data from a population pharmacokinetic model and each individual patient to estimate the patient's pharmacokinetic parameters. The a priori pharmacokinetic parameters of the population model are used as a starting estimate for the individual's parameters, which are then adjusted based on the patient's measured drug levels and with consideration of the variability of the parameters and drug concentration measurements. With this approach, the population model itself is incorporated into the estimation procedure.

This algorithm will determine the individual estimates of blood clearance (CI/F) and volume of distribution (Vd/F) from which the following PK parameters of HCQ exposure in individual patients will be calculated: 1) area under the concentration-versus time curve (AUC) 2) peak (Cmax) blood concentrations. 3) trough (Cmin) blood concentrations. AUC will be computed as follows: AUC (mcg * h/mL) = Dose (mg)/CI (L/h). The Cmin and Cmax levels will be derived from model-predicted concentrations just prior to and following a dose of HCQ, respectively. These data will be summarized by dose for the phase I portion of the trial and used for correlative toxicity and efficacy analyses.

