1.3 Correlative Objectives

- To evaluate the correlation between response to HCQ + B and pre-treatment tumor staining for PPT1, LC3, ALDH1A1, and HLTF by immunohistochemistry.
- To monitor changes on a repeat biopsy after 3 weeks of treatment with HCQ + B in PPT1, LC3, ALDH1A1, and HLTF by immunohistochemistry, as well as in gene signatures.
- To measure the change in median number of autophagic vesicles/cell (mAV/cell) in serially collected tumor tissue with HCQ + B.
- To determine if blood based candidate biomarkers of autophagy modulation (including IL-8, Interleukin-1 Beta, LIF, DKK3, and FAM3C, and other serum cytokines) reflect autophagy dynamics in tumors of patients treated with HCQ + B.
- To characterize HCQ pharmacokinetics when HCQ is combined with binimetinib
- To monitor changes in allelic fraction of KRAS in circulating tumor DNA (ctDNA) among patients treated with HCQ + B

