11.5 Plans for Data Analysis

Primary

- The objective response rate and 95% exact confidence interval will be calculated.
- All observed toxicities will be graded and tabled (worse grade experienced in all cycles). The
 overall rate of > grade 3 toxicity and 95% exact confidence interval will be calculated.

Secondary

• Progression-free survival and overall survival will be estimated by the method of Kaplan and Meier. Median values and 95% confidence intervals will be calculated.

Exploratory

- Associations between objective response and expression of biomarkers pre-treatment will be tested using nonparametric Wilcoxon rank sum test. Comparisons of pre- and post-treatment biomarker expression will be conducted using Wilcoxon signed ranks test for paired data.
- Describe autophagic vesicles/cell in tumor tissue at various time points using descriptive statistics and scatter plots.
- To evaluate HCQ pharmacokinetics and pharmacodynamics to determine whether changes in blood-based autophagy biomarkers (ctDNA KRAS allelic frequency) reflect tissue-based changes in autophagy (autophagic vesicles/cell), the nonlinear mixed–effects modeling approach (NONMEM) will be used to perform a full population PK analysis. PK-PD analyses to be conducted by University of Sciences of Philadelphia. Analysis methods – See Section 18. The key variables for the population include the Cmax and half life. Population PK will be assessed and qualitatively compared to population PK findings from other HCQ studies. No hypothesis testing will be performed for any of the vairables.

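### The HCQ population PK model can be read to pool patients on other HCQ combinations with no study or combination term, and its result is then compared only qualitatively, so HCQ exposure with binimetinib may not be isolated

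*Combined protocol and SAP*

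**What the plan says.** All references are to the combined protocol and SAP.

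- **Objective (1.3):** "To characterize HCQ pharmacokinetics when HCQ is combined with binimetinib".
- **Data for the model (7.2.3):** one model is fitted "over the entire patient population, which includes patients receiving HCQ in conjunction with other agents under investigation". The parameters named are CL/F and central Vd/F. No covariate for study or combination partner is mentioned.
- **Data for the model (7.2.1):** "Samples obtained during initial and late phases of the study will be used to build the population PK model". No outside dataset is mentioned here.
- **Individual exposure (7.2.3):** "The results from the population analysis will be used as prior information to obtain Bayesian estimates of each individual patient's PK parameters". AUC, Cmax and Cmin follow from these and feed the toxicity and efficacy correlations.
- **Comparison:** 7.2.1 compares this regimen with published values for HCQ alone. 7.2.3 words the same comparison for HCQ with D+T, and refers to a phase I portion. In 11.5 population PK will be "qualitatively compared to population PK findings from other HCQ studies", and "No hypothesis testing will be performed".
- **Use of the comparison (7.2.1):** a fuller interaction study becomes possible within a later, larger trial "If there is a significant difference between HCQ exposure in this study compared to previous studies" and there is sufficient activity.

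**The concern.** Every patient in this single-arm trial takes binimetinib with HCQ, so a model meant to describe HCQ with binimetinib needs only these patients, or a term that separates them from anyone else. The wording in 7.2.3 can be read as adding patients who take HCQ with different drugs. A single typical CL/F over such a mixture is an average across combinations, and that average then acts as the prior for the individual estimates. Sampling is sparse, at about one blood sample per monthly visit, so the prior may carry real weight.

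The comparison is also loose. Section 7.2.1 looks to a significant difference in HCQ exposure to motivate later interaction work. Neither 7.2.1 nor 11.5 names the exposure metric, the reference study or the size of difference that would matter. The reference moves from HCQ alone (7.2.1, 7.2.3) to other HCQ studies (11.5). The key quantities move from CL/F, Vd/F, AUC, Cmax and Cmin (7.2.3) to Cmax and half-life (11.5). Binimetinib PK is not planned, so this comparison is the trial's only PK look at an interaction.

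**Working it through.** The plan gives no PK sample size, margin or between-patient CV, so it has no PK figure to reproduce. What follows shows how the result depends on inputs that the plan leaves open.

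**Inputs.** This trial contributes n = 10 to 29 patients (11.6). The rest are assumptions: N = 30 to 100 outside patients; a true CL/F ratio r = 0.70 with binimetinib; no effect on HCQ of the outside patients' other drugs; shrinkage s = 10% to 50%; between-patient CV 30% to 50%.

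**1. Typical value, pooled with no covariate.** Treat the typical log CL/F as the average over patients, with w = n/(n + N). The apparent ratio is r^w.

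| n | N | w | 0.70^w |
|---|---|---|---|
| 10 | 30 | 0.250 | 0.915 |
| 10 | 100 | 0.091 | 0.968 |
| 29 | 30 | 0.492 | 0.839 |
| 29 | 100 | 0.225 | 0.923 |

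**2. Individual estimates from the pooled prior.** With shrinkage s toward the pooled mean, the trial-group average ratio is r^((1 − s) + s·w).

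- n = 29, N = 100: the exponent is 0.922, 0.767 and 0.612 at s = 10%, 30% and 50%, giving 0.72, 0.76 and 0.80.
- Lowest over the grid (n = 29, N = 30, s = 10%): 0.70^0.949 = 0.71.
- Highest over the grid (n = 10, N = 100, s = 50%): 0.70^0.545 = 0.82.

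The exponent is the share of the log effect that is kept, 55% to 95% over this grid. The individual estimates therefore keep more than half of the effect throughout, and the typical value keeps 9% to 49%.

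**3. Trial-only fit or a this-study covariate.** Here w = 1 and the ratio stays at 0.70.

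**4. Precision of a trial-only ratio to a fixed reference.** The 90% CI factor is exp(t(0.95, n − 1) × sqrt(ln(1 + CV²))/sqrt(n)).

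- n = 29: exp(1.701 × 0.2936/√29) = 1.10 at CV 30%; exp(1.701 × 0.4724/√29) = 1.16 at CV 50%.
- n = 10: exp(1.833 × 0.2936/√10) = 1.19 at CV 30%; exp(1.833 × 0.4724/√10) = 1.32 at CV 50%.

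These factors are optimistic. They treat each patient's CL/F as well estimated and the reference as known without error.

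**The case against.** The strongest reply is that no pooling is intended. Section 7.2.1 builds the model from samples taken in the study, 7.2.2 samples patients after the start of binimetinib plus HCQ, and no outside trial or number is named. Both D+T and a phase I portion are foreign to this trial, so the 7.2.3 text looks carried over from another protocol. Silence on covariates does not exclude them, and 11.5 sends the methods to a Section 18 that the document does not contain. This stands as far as it goes: pooling is uncertain. The instruction as written still does not say which data enter the model, and if it is carried over it describes another trial's analysis.

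A reader might infer that the method is biased toward finding no interaction. The documents do not support that. It requires that outside patients are pooled, that no covariate is used and that their other drugs leave HCQ unchanged. If those drugs do alter HCQ, the direction is unknown. Nor is harm to the correlations within this trial shown: all patients take binimetinib, so a common shift in the prior largely preserves their ordering.

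A reader might also infer that the condition in 7.2.1 cannot be evaluated because 11.5 rules out testing. That goes too far. Significant need not mean a hypothesis test, a descriptive comparison remains possible, and the condition is permissive and concerns a later study. What stands is that no criterion is given.

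**Conclusion.** The point holds in conditional form. Followed literally, 7.2.3 does not isolate HCQ PK with binimetinib, which is what 1.3 asks for, and 11.5 replaces an estimate of the difference with a qualitative comparison. Under the assumptions shown, a CL/F ratio of 0.70 would read 0.84 to 0.97 in the pooled typical value and 0.71 to 0.82 in the individual estimates. The true size cannot be stated, because the outside sample size and the shrinkage are not in the documents.

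A reader might want a fixed rule, such as the 90% CI lying wholly outside 0.80 to 1.25. The documents give no source for that margin. With a ratio of 0.70 and the factors above, the upper limits are 0.77 and 0.81 at n = 29 and 0.83 and 0.92 at n = 10 (CV 30% and 50%), so the rule would be met in only one of four cases.

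This is an exploratory, correlative matter. It does not touch the response-rate decision or the safety analysis, but it should be corrected because the correction is cheap.

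**What to change.** 1. In 7.2.3 and 11.5, state which patients enter the model. Base the HCQ-with-binimetinib estimates on this trial's patients alone or, if outside data are pooled, include a this-study (binimetinib) covariate on CL/F.
2. In 11.5, replace the qualitative comparison with the ratio of CL/F (or AUC) to a named reference HCQ dataset, with a 90% CI, labelled exploratory. Use the same metric and reference in 7.2.1 and 7.2.3.
3. In 7.2.1, refer to that estimate and interval in place of an undefined significant difference, without a fixed decision margin.
4. In 7.2.3, replace the D+T and phase I wording with text for this trial.

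The cost is a data-source statement, at most one covariate, and one interval in a model already planned. No new samples or visits are needed. Two limits must be stated with the result. The interval is wide if the trial stops at 10 patients. In a single-arm trial the binimetinib effect also cannot be separated from between-study differences in assay or population.

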4.0 TREATMENT PLAN

4.1 Overview

Patients will be treated with B 45 mg two times daily and HCQ 400 mg twice daily beginning on day 1. The dose of HCQ is based on an ongoing Phase 1 trial, and may be modified in a future amendment prior to the first patient enrolled. Efforts will be made to ensure dose homogeneity throughout the trial. Treatment will be administered on an outpatient basis on a 28 day cycle. Reported adverse events and potential risks for HCQ and B are described in Section 6. Appropriate dose modifications for HCQ and B are described in Sections 5 and 6. No investigational or commercial agents or therapies other than those described below may be administered with the intent to treat the patient's malignancy.

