4. Required q12 weeks (i.e. approximately every 3 cycles). ECHO to be performed between D21-D28 for applicable cycle

- Subjects who discontinue study treatment in the absence of disease progression will have post-treatment follow-up as per standard of care for disease status until one of the following events: (1) disease progression; (2) initiation of non-study cancer treatment; (3) withdrawal of study consent; (4) loss to follow-up; or (5) death. The subject will then enter into survival follow-up. Subjects who discontinue study treatment due to disease progression or initiation of a new anti-cancer therapy will enter survival follow-up directly. Survival follow-up will continue up to 1 year from initiation of study treatment (Cycle 1/Day 1).
- 6. RECIST 1.1 will be used in this study for assessment of tumor response. While either CT or MRI may be utilized, as per RECIST 1.1, CT is the preferred imaging technique in this study. Tumor imaging timing should follow calendar days and should not be adjusted for delays in cycle starts or extension of cycle duration. All visceral areas originally involved by tumor should be re-imaged at each scan interval. The preferred type of imaging is high resolution CT scans of the chest abdomen and pelvis with contrast. In cases of elevated creatinine or anaphylactic reaction to contrast dye, CT scans without contrast or MRI with gadolinium may be substituted for the abdomen and non-contrast CT for the chest.
- 7. The 30 day Safety Follow-up Visit must occur prior to the first dose of any new anti-cancer therapy.
- 8. Baseline tumor imaging to be performed within 30 days prior to Cycle 1/Day 1

UPCC 21520

- 9. Tumor imaging to be performed after every 2 cycles(approximately every 2 months after C1D1 on D21-D28 of applicable cycle).
- 10. CBC with differential including hemoglobin, white blood count, absolute neutrophil count, and platelet count. Serum chemistries including sodium (Na), potassium (K), chloride (Cl), bicarbonate (HCO3), blood urea nitrogen (BUN), creatinine (Cr), albumin, total bilirubin, AST, ALT, and alkaline phosphatase. After Cycle 1, pre-dose laboratory procedures can be conducted up to 72 hours prior to dosing. Results must be reviewed by the investigator or qualified designee and found to be acceptable prior to each dose of trial treatment.
- 11. Screening laboratory tests are to be performed within 10 days prior to Cycle 1/Day 1.

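### The HCQ AUC planned for the toxicity and efficacy correlations is Dose/Cl, a steady-state value not matched in time to early toxicity or first response; a fixed-window AUC would be a cheap improvement

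*Combined protocol and SAP*

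**What the plan says.** Section 7.2.3 obtains individual clearance and volume from a Bayesian population fit and derives three exposure measures from them. AUC is "AUC (mcg * h/mL) = Dose (mg)/CI (L/h"). Dose is not defined as per administration, per day, or as actually taken. For the other two: "The Cmin and Cmax levels will be derived from model-predicted concentrations just prior to and following a dose of HCQ, respectively". Which dose, or which day, is not stated. The measures are then to be "used for correlative toxicity and efficacy analyses".

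Section 7.2.1 says, after describing HCQ and its metabolites: "The mean elimination half-life of each of these metabolites is between 30-50 days". It also says that late samples best represent steady state.

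Section 4.1 fixes a common starting schedule with no loading phase: "Patients will be treated with B 45 mg two times daily and HCQ 400 mg twice daily beginning on day 1". The outcomes start early. Section 11.5 tabulates toxicity as "worse grade experienced in all cycles", which includes cycle 1. The study calendar places the first response scan near the end of cycle 2: "Tumor imaging to be performed after every 2 cycles(approximately every 2 months after C1D1 on D21-D28 of applicable cycle".

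**The concern.** Under linear kinetics, Dose/Cl is the AUC over one dosing interval at steady state. Every patient starts on the same dose, so at that dose it only orders patients by clearance. A drug with a half-life of weeks accumulates over months. Until it has accumulated, exposure depends largely on volume of distribution and time on drug, and clearance matters less.

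Toxicity in cycle 1 and response at the first scan are both observed during accumulation. Correlating them with a steady-state value pairs an early outcome with an exposure the patient did not yet have. A real association could be diluted, and at most 29 patients leave little room for that. No part of the plan defines an AUC matched in time to the outcome.

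**Working it through.** The documents give no figure for accumulation or time to steady state, so there is none to reproduce.

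**Inputs from the documents.** Half-life 30-50 days (Section 7.2.1). Cycle length: "Treatment will be administered on an outpatient basis on a 28 day cycle" (Section 4.1). First scan on days 21-28 of cycle 2, that is 28 + 21 = day 49 to 28 + 28 = day 56.

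**Assumptions.** One compartment, linear kinetics, constant twice-daily dosing, and the stated half-life applied to HCQ itself.

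**Step 1: share of steady state.** With k = ln 2 / half-life, the concentration at day t as a share of steady state is 1 - exp(-kt). Mean exposure from day 0 to t as a share of steady state is 1 - (1 - exp(-kt))/(kt).

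| | Half-life 30 days | Half-life 50 days |
|---|---|---|
| Concentration, day 28 | 48% | 32% |
| Concentration, day 49 | 68% | 49% |
| Concentration, day 56 | 73% | 54% |
| Mean exposure, days 0-28 | 26% | 17% |
| Mean exposure, days 0-56 | 44% | 31% |

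Dose/Cl overstates the current level by 1/0.476 = 2.1 to 1/0.322 = 3.1 times at day 28, and by 1/0.726 = 1.4 to 1/0.540 = 1.9 times at day 56. Steady state is 90% reached after ln 10 / k = 100 to 166 days.

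**Step 2: it is not a common scale factor.** Take two patients with equal volume and half-lives of 30 and 50 days. Their Dose/Cl differs by 50/30 = 1.67. Their actual levels differ by (50 × 0.322)/(30 × 0.476) = 1.13 at day 28 and (50 × 0.540)/(30 × 0.726) = 1.24 at day 56.

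**Step 3: effect on ranking.** Simulation of 200,000 patients with lognormal clearance and volume, a 40-day typical half-life and 30-50% CV (all assumed). Cumulative AUC to day t is proportional to (1/Cl)[t - (1 - exp(-kt))/k]. The table gives the approximate rank correlation of Dose/Cl with this AUC.

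| Correlation of log clearance and log volume | Day 28 | Day 56 |
|---|---|---|
| 0 | 0.2 | 0.4 |
| 0.5 | 0.6 | 0.7 |
| 0.8 | 0.84 | 0.88 |

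Unequal CVs (30% for one parameter, 50% for the other) widen the first row to 0.12-0.29 and 0.24-0.53.

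**Step 4: shorter half-life.** With clearance and volume independent and equal CVs, a 20-day half-life gives 0.36-0.38 at day 28 and 0.64 at day 56. A 10-day half-life gives 0.64 and 0.86-0.89. As a share of steady state, 15 days gives 73% at day 28 and 90-93% at days 49-56.

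**Step 5: which exposure window is safe.** Simulated trials of 29 patients with toxicity unrelated to pharmacokinetics. Assumed: 40% affected, onset uniform over days 5-112, unaffected patients followed to day 112, 40-day half-life, lognormal SD 0.4 for clearance and for volume. A 5% Wilcoxon test found a false association in about 98% of trials when cumulative AUC ended at toxicity onset, and in about 80% when mean concentration ended there. The rate was about 4% with Dose/Cl and 4-5% with a fixed window to day 56.

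**The case against.** Several counter-arguments have force.

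- **The half-life is worded for metabolites.** Whether it covers parent HCQ is unclear. A reader might infer that patients cannot be near steady state at the first scan. The documents do not establish that: at an effective half-life of about 15 days they would be at 90% or more. The cycle 1 mismatch survives shorter half-lives better.
- **The low rank correlations need independence.** A reader might conclude that Dose/Cl is only weakly related to actual exposure. That follows only if clearance and volume vary independently. Section 7.2.3 estimates apparent Cl/F and Vd/F, and unmodelled differences in bioavailability move both the same way. The documents give no correlation, so the weak-relation reading is one end of a range.
- **Cmax and Cmin are also planned.** They could be predicted at an early dose, and Section 7.2.1 links gastrointestinal toxicity to peak concentration. They would help, but the plan does not name the day.
- **Holds and reductions.** It is tempting to say that the formula ignores them. Because Dose is undefined and could mean the actual dose, the documents support only a request to define it.
- **The analysis is peripheral.** The sentence that sets up the correlations also mentions a phase I portion this trial does not have, and may be carried over. Section 11.5 names Cmax and half-life, not AUC, as key variables and plans no hypothesis tests on them.

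These points limit the size and importance of the concern. They do not supply an AUC that matches the outcome in time.

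**Conclusion.** The point stands as a minor, inexpensive improvement to an exploratory analysis. Dose/Cl is a correct steady-state formula; the weakness is its use, undated, against outcomes that arise during accumulation. On the stated half-life, and if it applies to HCQ, patients are at roughly a third to a half of steady state at the end of cycle 1 and at half to three quarters at first imaging. The effect on ranking could be serious (rank correlation about 0.2 at day 28) or modest (above 0.8), depending mainly on an unknown correlation between clearance and volume and on the true half-life. The response-rate endpoint and the two-stage decision do not use this quantity and are unaffected.

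**What to change.** In Section 7.2.3:

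- For the correlative analyses, use each patient's model-predicted cumulative AUC, or mean concentration, over a fixed window that is the same for everyone. Examples are days 0-28 for early toxicity and day 0 to the scheduled first scan (about day 56) for response. Compute it from the planned Bayesian Cl and Vd and the recorded dosing history.
- Do not end the window at toxicity onset. That ties exposure to event time, and it leaves exposure undefined for patients without toxicity.
- Interruptions prompted by a toxicity or by progression also lower recorded exposure later in the window. Report alongside it the value predicted at the assigned dose as a sensitivity analysis.
- State the day for which Cmax and Cmin are predicted, and define Dose.
- Keep Dose/Cl as a steady-state summary for comparison with other HCQ studies.

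The cost is a little post-processing of the planned population fit. The diary and last-dose times are already collected, no extra samples are needed, and treatment does not change.
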